## 7.3. Safety Endpoints

Safety analysis will include rate of complications and mortality and are categorical data sets. The chi-square test or Fisher's exact test will be used to assess the safety of IMT in combination with Prehab compared with its control i.e., standard Prehab using a significance level of 0.05.

The study may be ended prematurely, if there is a significant increase in post-surgical mortality or complications in the study group.

Additionally, if any of the patients in the intervention group experience syncope symptoms whilst using the device they will be advised to stop and will be withdrawn from the study.

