## 1. Introduction

### 1.1. Background

Lung cancer is the most common cause of cancer-related deaths in Wales (1). Although surgical resection for early-stage lung cancer with curative intent remains the primary treatment, patients with significant smoking related underlying cardiopulmonary disease and impaired pulmonary function, dyspnoea, frailty and decreased activity levels are unfit for surgery and referred for alternative treatment (2,3). Secondly, individuals who proceed to lung resection, thoracic surgery and general anaesthesia may have direct effects on their respiratory system potentially leading to postoperative pulmonary complications (PPCs), which increases hospital morbidity, prolongs hospital length of stay (HLOS) impacts on the quality of life (QOL) of patients and adds to health-care costs (4). Our aim is to evaluate whether incorporating a breathing training device, POWERBreathe into the existing standardised thoracic prehabilitation program (Prehab) will optimise unfit patients physically for surgery, and following surgery reduce their risk of developing PPC's, reduce HLOS and improve QOL of patients and improve service outcomes (5).

The PRIMROSE study aims to compare two groups of patients referred for Prehab who have lung cancer treatable with surgery: (A) standard Prehab and training with the inspiratory muscle training (IMT) device; and (B) standard Prehab alone, in non-small cell lung cancer patients (NSCLC) undergoing lung resection surgery, with clear primary and secondary outcome measures.

One hundred and thirty-four patients will be recruited for the study (67 for each arm) and with an anticipated attrition rate of 25%, one hundred patients will finally be studied (6,7). With 134 recruited and an attrition rate of 25%, only 100 will remain (50 in each arm). The primary outcome measure tested will be the proportion of patients in each group experiencing postoperative pulmonary complications (PPC), which will be graded I-V using the Clavien Dindo Classification (8). PPCs will be broadly classified as minor (grade 1) and major complications (grade 2-5 where 5 is death). What we want to learn from this RCT study is whether IMT helps reduce grade  $\geq 2$  PPCs to either grade 1 or no complications and thereby help shorten the length of stay in hospital for patients undergoing lung resection surgery.

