## 2.4. Statistical Methodology and Analysis

### 2.4.1. Sample size, justification and calculations

Our literature search did not bring up a suitable RCTs on the use of POWERBreathe Inspiratory Muscle Trainer (IMT) in lung resection patients. Hence, we used the outcome data from the RCT on cardiac patients on whom POWERBreathe IMT was used and we have experience with. We acknowledge that the cardiac surgery patient population are very different and do not accurately reflect our study population (as patients undergoing cardiac surgery do not undergo lung resection). There is one RCT on the use of inspiratory spirometry used in patients undergoing lung resection in order to strengthen their diaphragm function prior to surgery (29). Inspiratory muscle training using inspiratory spirometry is different to the POWERBreathe IMT. However, the patient population and design of this RCT are more in line with our PRIMROSE Trial, making it more pertinent to use the data from this RCT instead of the RCT in a cardiac population. Hence, using the data from the lung resection patient trial, and assuming a 36.7% incidence of PPC after surgery in the control arm and using a significance level of 0.05 and a power of 80%, the online calculator estimates 50 patients are required in each arm of the study (Figure 5).

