#### **2.4.2 Analysis Plan**

Our aim is to evaluate the impact of thoracic Prehab with IMT compared to standard Prehab in reducing post operative pulmonary complications following surgical resection in lung cancer patients in a RCT.

The analysis will include descriptive data (means and standard deviation) on all outcomes collected, including levels of missing data, leading to the calculation of clinically important differences. Descriptive statistics will be used to summarise participants' baseline characteristics and outcome measures.

Statistical analyses will be performed using SPSS statistical software, version 20.0 (IBM Corporation, Armonk, NY, USA). Two-sided significance tests will be used ( $\alpha \leq 0.05$ ). Data will be presented as mean and standard deviation (SD), or median and interquartile range (IQR) for variables with a skewed distribution. Differences between groups in categorical variables will be tested with Chi square or Fisher's exact test. For continuous data the student's t test or the Mann-Whitney U test will be used. The Wilcoxon signed rank test will be used to compare MIP and QoL at T0 and T1 and T3. Relative risk will be calculated for post operative pulmonary complications (PPCs) graded 1-V using the Clavien Dindo classification and impact of IMT on the study group compared to the control group. Assuming a 36.7% incidence of PPC after surgery in the control arm and using a significance level of 0.05 and a power of 80%, 50 patients are required in each arm of the study for analysis."

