## 7.5. Statistical Analysis

Our aim is to evaluate the impact of thoracic Prehab with IMT compared to standard Prehab in reducing post operative pulmonary complications following surgical resection in lung cancer patients in a RCT. Statistical analysis will be performed using SPSS statistical software, version 20.0 (IBM Corporation, Armonk, NY, USA). Two-sided significance tests will be used ( $\alpha \leq 0.05$ ). Data will be presented as mean and standard deviation (SD), or median and interquartile range (IQR) for variables with a skewed distribution. Differences between groups in categorical variables will be tested with Chi square or Fisher's exact test.

For continuous data the student's t test or the Mann-Whitney U test will be used. The Wilcoxon signed rank test will be used to compare MIP and QoL at T0 and T1 and T2.

Relative risk will be calculated for post operative pulmonary complications (PPCs) graded 1-V using the Clavin Dindo classification and impact of IMT on the study group compared to the control group. Assuming a 36.7incidence of PPC after surgery in the control arm and using a significance level of 0.05 and a power of 80%, 50 patients are required in each arm."

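### Section 7.3 gives only a significance test at 0.05, with no interval, as the between-arm method for safety; a non-significant result could be read as safe, which the test cannot support at this sample size

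*Protocol*

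**What the plan says.** Protocol section 7.3 names the safety endpoints: "Safety analysis will include rate of complications and mortality and are categorical data sets". It then fixes the comparison: "The chi-square test or Fisher's exact test will be used to assess the safety of IMT in combination with Prehab compared with its control", that is, "standard Prehab using a significance level of 0.05". Section 7.5 adds that "Two-sided significance tests will be used". No confidence interval, tolerable excess or power for harm is given for either endpoint.

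The sample size in section 2.4.1 concerns benefit on postoperative pulmonary complications (PPCs) only: "assuming a 36.7% incidence of PPC after surgery in the control arm", "using a significance level of 0.05 and a power of 80"%, leading to 50 per arm. Section 1.1 gives the recruitment figure: "With 134 recruited and an attrition rate of 25%, only 100 will remain (50 in each arm"). Sections 2.4.2 and 7.5 also plan a relative risk for PPCs, without mentioning an interval. Section 2.4.1 schedules mortality at discharge, 1 month, 3 months and 365 days.

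**The concern.** The null hypothesis of the test in section 7.3 is no difference between arms. Rejecting it towards more events on IMT would show harm. Failing to reject it shows only that the data were insufficient to reject. Because section 7.3 pairs the aim of assessing safety with a test and a significance level, and gives nothing else for comparing the arms, a report that follows it could offer a p-value above 0.05 as its safety finding.

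That matters in this trial for three reasons. The number of patients was chosen for a benefit on PPCs, not to detect harm. Section 1.4 expects no risks to participants, while section 5.1.1 lists pneumothorax as a possibility with the device, so a null result could be taken to confirm section 1.4. Section 12 plans to share the findings with other Health Boards and NHS Trusts, so any false reassurance would travel.

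The point concerns the final safety comparison, not the early-stopping sentence in the same section.

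**Working it through.** **Inputs from the protocol.** 50 per arm (2.4.1); 67 per arm randomised (1.1); two-sided 0.05 (7.3, 7.5); control PPC rate 36.7% (2.4.1), used as a stand-in because no overall complication rate is given.

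**Assumptions.** The protocol gives no mortality rate, so control rates of 2%, 3% and 5% are assumed. It does not say when Fisher replaces chi-square; I used uncorrected chi-square, and Fisher where an expected count is below 5.

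**The plan's own figure.** 50/(1 − 0.25) = 66.7, rounded up to 67 per arm and 134 in all, which agrees with section 1.1. The 50 itself cannot be reproduced forwards, because the readable text gives no IMT-arm rate. Solving backwards with the pooled two-sided formula, 50 per arm corresponds to about 12.6% to 12.8% on IMT. Nothing below depends on this.

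**Chance of missing a true excess.** For n per arm and true rates p_C and p_I,

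power for harm = Σ_a Σ_b Bin(a; n, p_C) × Bin(b; n, p_I) × 1[b/n > a/n and p-value ≤ 0.05],

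summed over all pairs of counts; the chance of missing is 1 − power.

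| True rates, control to IMT | Power, n = 50 | Missed, n = 50 | Power, n = 67 | Missed, n = 67 |
|---|---|---|---|---|
| Complications 36.7% to 46.7% | 0.180 | 82% | 0.207 | 79% |
| Complications 36.7% to 56.7% | 0.543 | 46% | 0.634 | 37% |
| Mortality 2% to 6% (assumed) | 0.034 | 97% | 0.083 | 92% |
| Mortality 3% to 9% (assumed) | 0.111 | 89% | 0.227 | 77% |
| Mortality 5% to 10% (assumed) | 0.093 | 91% | 0.169 | 83% |
| Mortality 2% to 10% (assumed) | 0.210 | 79% | 0.398 | 60% |

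**Sensitivity to the choice of test (n = 50).** With Fisher throughout, the two complication rows are missed 87% and 54% of the time. With uncorrected chi-square throughout, mortality 2% to 6% is missed 86% of the time and 2% to 10% 62%.

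**Observed results that would be non-significant at n = 50.**
- Deaths, 5/50 on IMT against 0/50: Fisher p = 2 × C(50,5)/C(100,5) = 2 × 2,118,760/75,287,520 = 0.056.
- Complications, 27/50 against 18/50: the pooled rate is 0.45, so chi-square = 0.18²/(0.45 × 0.55 × 2/50) = 0.0324/0.0099 = 3.27, p = 0.070. The observed excess is 18 points.

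**What an interval would show.** With Wilson limits (l, u) for each arm, the Newcombe upper limit for IMT minus control is d + √[(u_I − p_I)² + (p_C − l_C)²].
- 18/50 in each arm: Wilson 24.1% to 49.9%; upper limit √(13.86² + 11.86²) = 18.2 points.
- 1/50 in each arm: Wilson 0.35% to 10.50%; upper limit √(8.50² + 1.65²) = 8.7 points.
- 0/50 in each arm: Wilson 0% to 7.1%; upper limit 7.1 points.
- 27/50 against 18/50: difference 18 points, 95% interval −1 to +36.
- 5/50 against 0/50: difference 10 points, 95% interval +1 to +21.

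**The case against.** The strongest objection is that the protocol contains no pass rule. A reader might infer from section 7.3 that p > 0.05 will count as safe, but no sentence says so, and assessing safety with a test is equally consistent with looking for a harm signal. This stands: the documents support a risk of misreading, not a stated false conclusion.

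A reader might also infer that the whole safety evaluation rests on one p-value. It does not. Sections 5 and 6 provide for case-by-case assessment and reporting of adverse events, section 10 gives the trial management group a review of safety data, section 2.4.2 promises descriptive data on all outcomes, and the PPC relative risk overlaps the safety endpoints, since grade V is death. None of these, however, gives an interval for the between-arm difference in complications or mortality.

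Intervals are often left to a statistical analysis plan, and one may exist unseen. Their absence alone would be no finding. Here the protocol itself fixes the comparative method, and its wording would stand beside any such plan.

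The mortality figures depend on assumed rates. Section 4.12 promises that all patients enter an intention-to-treat analysis, which could argue for 67 per arm. These endpoints arise after surgery, so 50 is the reasonable base; with 67 the chances of missing an excess fall but remain large. Finally, low power for harm is common in trials sized for efficacy, and the change below adds no power.

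**Conclusion.** The point holds in a limited form. The only between-arm method stated for safety is a two-sided test at 0.05 without an interval, and a non-significant result from it cannot support a conclusion that IMT is safe. At 50 per arm, a 10-point excess in complications would go undetected about four times in five and a 20-point excess nearly half the time; at the assumed rates, a tripling of mortality from 2% would almost always be missed. The complication figures rest on the PPC rate standing in for all complications, the mortality figures on assumed control rates, and both on the stated rule for choosing between chi-square and Fisher. The primary efficacy test is unaffected. This should be corrected, but it is a matter of how safety is summarised and interpreted, not evidence that the trial is unsafe or will claim safety wrongly.

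**What to change.** In section 7.3, replace the test sentence with wording such as: 'Safety will be described by the between-arm risk difference (IMT minus control) in complications and in mortality, the latter at each planned time point, each with a two-sided 95% Newcombe (score) confidence interval. The upper limit will be reported as the largest excess that the data do not rule out. A non-significant p-value will not be taken as evidence of safety.'

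Add a note that at 50 per arm even equal observed rates leave an upper limit of about 18 points for complications (18/50 each) and 7 to 9 points for deaths (0 or 1 of 50 each). The chi-square or Fisher p-value may stay as description. It can disagree with the interval at small counts, as 5 deaths against 0 shows, so the interval should be named as the main summary.

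The cost is a few sentences, with no new data, patients or staff. The downside is that the report can make only a limited safety statement.

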**Post-discharge assessment:** Our primary objective is to determine whether IMT prior to surgery with Prehab helps reduce PPC following surgery, which is up to the point of discharge from hospital (alive or dead). This is one time point. Hence, it is anticipated that all patients will complete the discharge assessment for complications. Thus, the study is not underpowered for the primary end point.

Mortality rates will be collected at discharge, 1 month, 3 months, and 365 days post-surgery.

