### 3.3. Exclusion Criteria:

- Inclusion criteria not met
- Patients who have undergone recent abdominal surgery and those with an abdominal hernia
- Patients diagnosed with other cancers namely, patients with metastatic lung cancer, mesothelioma, sarcoma, mediastinal tumours, or benign diseases
- Patients who decline Prehab
- Patients who do not consent to Prehab, do not attend or have died prior to commencing Prehab. Patients who do not consent to surgery.
- Patients with a high cardiovascular risk for Prehab and awaiting investigations or interventions (including unstable angina and syncope)
- Patients with a serious concomitant disorder that would compromise patient safety during Prehab
- Patients with a history of spontaneous pneumothorax and/or evidence of large bullae on radiological imaging
- Patients who have suffered from or likely to suffer from costochondritis
- Patients with marked osteoporosis with history of rib fractures
- Patients with pulmonary hypertension
- Patient with a perforated ear drum
- If a participant is involved in a study similar, with potential to cause bias or conflict of interest then they will be excluded
- Patients with worsening heart failure signs and symptoms after IMT

To prevent the transmission of respiratory infections, the research team will advise patients not to share the device with family members. If patients are suffering from a cold, sinusitis or respiratory tract infection they will be advised not to use the device until their symptoms have resolved.

Participants who do not understand written and/or spoken English can access a translator through the health board.

The research team will collect a list of patients that decline to participate in the trial, to assess recruitment rates at the end of the study.

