**Cardiovascular exercises:** namely, stationary cycle ergometry and upper and lower limb resistance exercises will be performed, whilst monitoring the heart rate, blood pressure and oxygen saturations (15). The rate of perceived exertion (RPE) will be measured using the Borg breathlessness scale and used twice at every session to measure the intensity at which each patient is working and guide them to increase or decrease their effort as required.

**Home Exercise Program (HEP):** individualised home exercise programme includes daily walking plan and stair climbing exercise (15). Training enabling them to maintain activities of daily living following surgery. The HEP will be continued following discharge after surgery.

**Health education and smoking cessation advice** will be provided to all current smokers prior to surgery and support following surgery (15). Where necessary nicotine replacement therapy will be provided.

**Intervention group:** The intervention group will receive IMT in addition to a standard Prehab protocol (as above). An MIP in cmH2O, obtained at or greater than 1.5 seconds will be recorded, and the highest MIP of 3 valid breaths will be used as baseline. The IMT pressure in cmH2O will be set initially at 40% of the patients MIP. Participants will be taught to use the device in an upright position and instructed to perform six sets of six breaths with the resting times between each set of breaths reducing from 60 seconds, to 45 seconds, to 30 seconds, to 15 seconds, to 5 seconds. IMT will be used twice-daily preoperatively in the intervention group and not post operatively. Training load intensity on the IMT will be

increased preoperatively by the patient according to the rate of perceived inspiratory effort, on a modified Borg scale.

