#### 4.5. Schedule of Assessment (in Diagrammatic Format)

Figure 6 describes the time points at which assessments and data will be collected.

Measure	Researcher or participant completing	At assessment (T0)	Every two weeks of Prehab	On Prehab Completion (T1)	At hospital discharge (T2)	1 month post-op (T3)	3 month post-op (T4)	1 year post-op (T5)
EORTC QLQ-C30	Participant	+	-	+	+	+	+	-
Dyspnoea score	Researcher	+	+	+	+	+	-	-
PS	Researcher	+	+	+	+	+	-	-
Thoracoscore	Researcher	+		+	-	-	-	-
Frailty index	Researcher	+	+	+	+	+	-	-
LOA	Researcher	+	+	+	+	+	-	-
Researcher	Researcher	+	+	+	+	+	-	-
MIP	Researcher	+	-	+	+	-	-	-
FEV1	Researcher	+	-	-	-	-	-	-
TLCO	Researcher	+	-	-	-	-	-	-
HLOS (days)	Researcher	-	-	-	+	-	-	-
Mortality	Researcher	-	-	-	+	+	+	+
Post-op complications	Researcher	-	-	-	+	-	-	-

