### 5.1. General Definitions

#### 5.1.1. Adverse Event (AE)

An AE is any untoward medical occurrence in a subject which is not necessarily caused by or related to the study. An AE can therefore be any unfavourable and unintended sign (including an abnormal laboratory finding), symptom or disease temporarily associated with study activities. There is a possibility of dizziness, coughing, tiredness and a pneumothorax with the inspiratory muscle trainer device.

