## 6.2. Notification and reporting Adverse Events or Reactions

If the AE is not defined as SERIOUS, the AE is recorded in the study file and the participant is followed up by the research team. The AE is documented in the participants' medical notes (where appropriate) and the CRF.

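### IMT is used only before surgery, but the one stated between-arm safety analysis rests on data scheduled only after surgery

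*Protocol*

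**What the plan says.** The exposure is confined to the period before surgery. Protocol Section 4.4 states: "IMT will be used twice-daily preoperatively in the intervention group and not post operatively".

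The protocol names harms of the device. Section 5.1.1 says: "There is a possibility of dizziness, coughing, tiredness and a pneumothorax with the inspiratory muscle trainer device". Section 7.3 adds syncope during use, which leads to withdrawal of that participant. Section 3.3 lists among the exclusions: "Patients with worsening heart failure signs and symptoms after IMT".

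The safety analysis is set out in Section 7.3: "Safety analysis will include rate of complications and mortality and are categorical data sets". These are compared between arms by chi-square or Fisher's exact test, as a test of the safety of IMT. The stopping sentence follows: "The study may be ended prematurely, if there is a significant increase in post-surgical mortality or complications in the study group".

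On data collection, Figure 6 (Section 4.5) has a single complications row, labelled "Post-op complications" and marked only at hospital discharge (T2). Mortality is marked from T2 to T5. Section 2.4.1 agrees: "Mortality rates will be collected at discharge, 1 month, 3 months, and 365 days post-surgery". Figure 6 has no adverse-event row at T0, during Prehab or at T1.

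Non-serious adverse events are handled in Section 6.2: "The AE is documented in the participants' medical notes (where appropriate) and the CRF". Serious events are reported individually under Sections 5.1.2 and 6.3.

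**The concern.** The safety test is meant to judge IMT, but the data scheduled for it begin after exposure has ended. Section 4.10 itself says that a pre-operative intervention will not affect post-operative safety. Followed as written, the comparison therefore looks where the protocol expects no device effect and leaves out the weeks in which one would be expected.

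Reaching surgery is also an event after randomisation. Under Section 3.4 a participant can be withdrawn for an adverse cardio-respiratory event, or because the MDT no longer considers resection suitable. Such a participant has no T2 visit and adds nothing to the complication rate. A death before surgery has no mortality time point either. At stake is whether the trial can say anything comparative about harm during device use.

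**Working it through.** **Timing, set side by side**

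| Item | Before surgery | After surgery |
|---|---|---|
| IMT use (4.4) | Twice daily, intervention arm | None |
| Named device harms (5.1.1, 7.3, 3.3) | Mainly here | Only if they persist or appear late |
| Complications in Figure 6 | Not scheduled | T2 only |
| Mortality in Figure 6 and 2.4.1 | Not scheduled | T2 to T5 |
| Individual adverse-event recording (6.2) | Yes | Yes |
| Stated between-arm comparison (7.3) | No scheduled data to feed it | Yes |

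The intention-to-treat statement in Section 4.12 keeps withdrawn participants in the analysis. It does not create a pre-operative safety outcome on which to analyse them.

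**The plan's own figure**

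Inputs are 50 per arm and 25% attrition (Sections 1.1 and 2.4.1). 50 / (1 − 0.25) = 66.7, rounded up to 67 per arm, or 134 in total. This reproduces the stated target.

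**Who may lack a post-surgical record**

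Section 2.1 anticipates 20-25% attrition: 134 × 0.20 = 26.8, about 27; 134 × 0.25 = 33.5, about 34. This is attrition from all causes. Section 2.1 bases it partly on 6.8% who do not attend Prehab and 1.1% who die before it starts, and those people would have little or no IMT exposure. So 27 to 34 is a ceiling, provided the attrition estimate holds.

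**What a comparison in all randomised patients could show**

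The documents give no rate of device harm, so the rates below are assumptions. There are 67 per arm.

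- With 0 events in 67, the two-sided exact 95% upper limit is 1 − 0.025^(1/67) = 5.4%.
- The chance of at least one event in 67 is 1 − (1 − p)^67: 49% for p = 1%, 74% for 2% and 97% for 5%.
- For k events against 0 in equal arms, the two-sided Fisher p-value is 2 × C(67,k) / C(134,k): 0.24 for k = 3, 0.058 for k = 5 and 0.028 for k = 6. Six against none is the smallest such split with p < 0.05.
- Fisher power is 0.2% for 2% v 0%, 12% for 5% v 0% and 67% for 10% v 0%.

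For rare harms, rates with exact intervals therefore carry more information than a test.

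**The case against.** The case against has real substance.

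- **The wording is open.** Section 7.3 says the analysis will include complications and mortality, which is not exhaustive, and it does not qualify complications there. In the stopping sentence, post-surgical could be read as applying to mortality alone. A reader might infer that device harms are shut out of every safety comparison. The text does not go that far. What stands is that the schedule supplies no other complications data.
- **Oversight exists.** Adverse events are defined, graded for severity and recorded in the study file and CRF (Sections 5.1.1, 6.1.4 and 6.2). Urgent safety measures are available (6.4), the chief and principal investigators review data monthly (8.4), and the trial management group reviews safety data (Section 10). A reader might infer that the trial cannot respond to harm before surgery; these provisions contradict that. The stopping sentence is permissive and does not claim to be the only ground for ending the study. What is missing is systematic collection alike in both arms and a comparison by arm.
- **Adverse-event tables may sit in a SAP.** That is fair for table layouts. But the protocol itself fixes the safety endpoint and the collection schedule, and a later SAP could not fully make up for events not asked about alike in both arms.
- **A comparison would have little power.** True, as the working shows. This argues for descriptive rates and intervals, and for a moderate severity.

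**Conclusion.** The point holds as a mismatch between when the device is used and when the data for the stated safety comparison are scheduled. Followed as written, a safety conclusion would be conditional on reaching surgery and would undercount device events before it. This rests on reading complications in Section 7.3 through Figure 6, the only place where their collection is scheduled.

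Two stronger readings are not supported. A reader might infer that the selection biases the safety result in favour of IMT. Undercounting of pre-operative events is supported, but the net direction for post-operative complications is unknown. The protocol hopes IMT will make unfit patients fit for surgery (Section 1.1), and if more frail IMT patients were operated on, the bias could run the other way. A reader might also take 27 to 34 of 134 as the number harmed or missed because of the device. It is an all-cause ceiling.

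Severity: should-fix.

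**What to change.** In Section 7.3, state that the following will be summarised by arm in all randomised patients: pre-operative adverse events, serious adverse events, each device harm the protocol names, and deaths timed from randomisation. Present them as rates with exact confidence intervals, without relying on a significance test for rare harms.

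Add one adverse-event row to Figure 6 at the existing Prehab sessions and at T1, with the same questions put in the same way to both arms.

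The sponsor should also reconcile Sections 3.3, 4.4, 4.5, 5.1.1, 6.2 and 7.3. Two items need attention: the exclusion criterion that can arise only once IMT has begun, and the post-surgical wording of the stopping sentence set against pre-operative exposure. No eligibility or stopping rule is proposed here; their content is for the sponsor.

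The cost is protocol wording, one schedule row, one extra table and a few minutes of questions per session. The sessions and CRF recording already exist.
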